8.3. Visit 2: Two Week Touch-up Visit

The following procedures will be performed:

1. At PI's discretion, subjects may receive touch-up treatment to reach Optimal Cosmetic Result (OCR) (not to exceed a total use of 4mL/4 syringes of *Restylane® Defyne*).
2. Subject will report any AE or Concomitant medications

8.4. Visit 3: One Month Follow-up Visit

The following procedures will be performed:

1. Subject will undergo standardized 2D digital portrait photography.

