1 PROTOCOL SYNOPSIS**TITLE:**

Premaxillary injection for perioral rejuvenation and upper lip enhancement

INDICATION:

Premaxillary injection performed via cannula technique for perioral rejuvenation

SAMPLE SIZE:

20

NUMBER OF CENTERS:

One

PURPOSE:

To determine if subjects who receive premaxillary injection demonstrate an increase in nasal tip projection and an associated increase in upper lip projection, and vermillion height.

SUBJECTION SELECTION:

A total of 20 subjects who display signs of perioral aging or poor upper lip projection

PROCEDURE:

This is an open-label, prospective, post market study to assess the effect of premaxillary hyaluronic acid filler injection on nasal tip projection and upper lip position.

The study will enroll and treat a total of 20 subjects who are filler naïve and do not have any history of rhinoplasty, recent upper lip augmentation <12 months, lip lift or other surgical procedures involving the upper lip, chin augmentation and orthognathic surgery. Patients in study are restricted from perioral neurotoxin, peri oral ablative resurfacing, facial cosmetic surgery, all subdermal directed aesthetic treatments or filler treatment other that which is dictated in the protocol during the course of the study.

Subjects, who fulfill all eligibility criteria, will undergo pre-treatment standardized 2D portrait photography. From the profile image, baseline nasal projection measurements will be documented according to Goode's ratio. Additionally, baseline upper lip position will recorded by measuring the Z-angle, which is the intersection of the Frankfort horizontal line and the profile line as described by Merrifield. From the straight portrait image, the ratio of the upper lip vermillion height to the lower lip vermillion height will be documented. Subjects will then be injected with a maximum of 4 syringes of Restylane® Defyne to treat their premaxillary space per the discretion of the Principal Investigator (PI). If optimal correction result (OCR) has not been achieved additional touch-up injections of Restylane® Defyne may be injected 2 weeks post treatment visit to achieve OCR as per PI discretion.

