Post OCR visits will be performed at 4 weeks following premaxillary injections. Subjects will be followed to assess any treatment-related adverse events (such as pain, nodules, swelling, redness, bruising, tenderness, itching, and headache) as well as pigmentation changes and/or keloid formation. Each subject will then be photographed with standardized photographs in a similar fashion as pre-treatment and the same measurements will be recorded.

Upon study culmination, pre-treatment and 1-month post OCR photographs will be assessed. Each patient will be evaluated to determine if nasal tip projection was increased causing an increase in upper lip projection. Additionally, the vermilion ratios will be compared to evaluate for change in upper lip vermilion height.

STUDY DURATION:

Each subject will undergo screening assessment of eligibility criteria, pre-treatment photography, and if eligible for treatment, injections of the premaxillary area. All enrolled subjects will be followed up to 1-month post OCR visit to evaluate the injections effect on nasal tip projection and upper lip projection.

OBJECTIVES:

The Primary Objective of this study is to determine the increase in nasal tip projection (measured by Goode's ratio) and the increase in upper lip projection (measured by the Z-angle) following perioral rejuvenation with premaxillary hyaluronic acid filler injections.

The Secondary Objective of this study is to assess the change in upper lip height by comparing the pre and post-treatment injection ratio of upper lip vermilion height to lower lip vermilion height.

CLINICAL HYPOTHESES:

Subjects who are treated with premaxillary injection will demonstrate an increase in nasal tip projection and have an associated increase in upper lip projection. Additionally, the upper lip will demonstrate an increase in upper lip vermilion height. As a result, the single injection site will address multiple factors that contribute to perioral aging.

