5 STUDY DESIGN

This is an open-label, prospective, postmarket study to assess the effect of premaxillary hyaluronic acid filler injection on nasal tip projection and upper lip position.

The study will enroll and treat a total of 20 subjects who are filler naïve and do not have any history of rhinoplasty, recent, 6 months upper lip augmentation, lip lift or other surgical procedures involving the upper lip, chin augmentation and orthognathic surgery. Patients in study are restricted from perioral neurotoxin or ablative resurfacing, facial cosmetic surgery, all subdermal directed aesthetic treatments or filler treatment other than which is dictated in the protocol during the course of the study.

Subjects, who fulfill all eligibility criteria, will undergo pre-treatment standardized 2D portrait photography. From the profile image, baseline nasal projection measurements will be documented according to Goode's ratio. Additionally, baseline upper lip position will be recorded by measuring the Z-angle, which is the intersection of the Frankfort horizontal line and the profile line as described by Merrifield. From the straight portrait image, the ratio of the upper lip vermilion height to the lower lip vermilion height will be documented. Subjects will then be injected with a maximum of 4 syringes of Restylane® Defyne to treat their premaxillary space per the discretion of the Principal Investigator (PI). If optimal correction result (OCR) has not been achieved additional touch-up injections of Restylane® Defyne may be injected 2 weeks post treatment visit to achieve OCR as per PI discretion.

Post OCR visits will be performed at 4 weeks following premaxillary injections. Subjects will be followed to assess any treatment-related adverse events (such as pain, nodules, swelling, redness, bruising, tenderness, itching, and headache) as well as pigmentation changes and/or keloid formation. Each subject will then be photographed with standardized photographs in a similar fashion as pre-treatment and the same measurements will be recorded.

Upon study culmination, pre-treatment and 1-month post OCR photographs will be assessed. Each patient will be evaluated to determine if nasal tip projection was increased causing an increase in upper lip projection. Additionally, the vermilion ratios will be compared to evaluate for change in upper lip vermilion height.

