8.2. Visit 1: Baseline/Treatment Procedures

The following procedures will be performed:

1. The injection area will be wiped with a Benzalkonium Chloride towlette.
2. A topical anesthetic containing lidocaine (30%) will be applied to anesthetize injection areas Or subject may choose to receive a nerve block to numb the treatment area.

3. The subject will be injected with *Restylane® Defyne* in a volume sufficient to deliver satisfactory cosmetic results (not to exceed 4mL/4syringes total).
4. The volume injected into each area will be recorded.

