9 RESPONSE CRITERIA

9.1 Primary Variable Assessments

The primary assessment of this study is to determine the effect of premaxillary injection on nasal tip projection and upper lip projection for perioral rejuvenation. Efficacy of the injection on the subjects' 1-month post OCR with *Restylane® Defyne* will be done through comparative measurements taken on pre and post-treatment photographs.

Nasal tip projection will be assessed by Goode's ratio. The value is defined as nasal height over the nasal length. The nasal height is measured from the alar-facial groove to the tip-defining point and the nasal length is measured from the root of the nose, or nasion, to the tip-defining point. Upper lip projection will be measured by a method outlined by Merrifield in 1966. As described, a profile line is drawn tangent to the soft tissue chin and to the most anterior point of the upper lip. This line is then extended upward to the Frankfort horizontal plane. The angle at which these two lines intersect is called the Z angle. A change in the angle to a more acute value on postoperative photographs would indicate an increase in upper lip projection. This method was chosen because it is calculated independent of any postoperative nasal changes.

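### Does the one-month label in Section 8.4 leave it open whether the efficacy photograph is timed from OCR or from the first treatment?

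*Combined protocol and SAP*

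**What the plan says.** Section 8 lists three study visits after screening: "Visit 1: Baseline/Treatment Procedures", "Visit 2: Two Week Touch-up Visit" and "Visit 3: One Month Follow-up Visit". The third has one listed procedure, the portrait photography. Neither its heading nor that procedure mentions OCR, and no visit window is given.

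The starting point of the two-week visit comes from elsewhere. The Synopsis, and Section 5 in the same words, says that a touch-up "may be injected 2 weeks post treatment visit to achieve OCR as per PI discretion".

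The timing of the follow-up visit is set in the Synopsis and in Section 5: "Post OCR visits will be performed at 4 weeks following premaxillary injections". The efficacy time point is then stated relative to OCR in three places:

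- Synopsis, Study Duration: "All enrolled subjects will be followed up to 1-month post OCR visit".
- Section 5 (and the Synopsis, Procedure): "pre-treatment and 1-month post OCR photographs will be assessed".
- Section 9.1, the primary assessment: "Efficacy of the injection on the subjects' 1-month post OCR with" the study product, measured on photographs from before and after treatment.

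**The concern.** The visit list is what site staff tend to work from, and there the reference to OCR is missing. A two-week visit followed by a one-month visit looks like one running clock, and the two-week visit is counted from Visit 1. The sentence that sets the follow-up at four weeks does not fully close the question. It calls the visit post-OCR but counts from the injections without naming a session, and a touched-up subject has two sessions.

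Both primary measurements (Goode's ratio and the Z-angle) and the secondary vermilion ratio are read from the Visit 3 photograph. Section 8 lists no other post-treatment photograph that could replace one taken at the wrong time. If the month were counted from Visit 1, the paired t test of Section 11.3 could combine photographs taken at clearly different times after OCR, although the plan names one time point. Swelling is among the treatment-related events to be followed, so the time since the last injection is not an idle detail.

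**Working it through.** The plan states no figure for this interval in days, so there is nothing to reproduce first. The check has two parts: the day arithmetic under each count, and a comparison of the passages to see which count the document supports.

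**Inputs**

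- Visit 1 is day 0 (Section 8.2).
- A touch-up, if given, is on day 14 (Synopsis; Sections 5 and 8.3).
- One month, *m*, is 28 days, from the four weeks in the Synopsis and Section 5. Values of 30 and 31 days are shown as alternatives.

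**Formula**

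Days from OCR to photograph = Visit 3 day − OCR day.

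**Subject who reaches OCR at the touch-up (OCR day = 14)**

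| *m* | Counted from Visit 1: days after OCR | Counted from OCR: study day | Counted from OCR: days after OCR | Shortfall |
|---|---|---|---|---|
| 28 | 28 − 14 = 14 | 14 + 28 = 42 | 28 | 14 (14/28 = 50%) |
| 30 | 30 − 14 = 16 | 14 + 30 = 44 | 30 | 14 (14/30 = 47%) |
| 31 | 31 − 14 = 17 | 14 + 31 = 45 | 31 | 14 (14/31 = 45%) |

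**Subject not touched up**

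The document does not date OCR for these subjects, so two assumptions are shown.

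- OCR dated to Visit 1 (day 0): both counts put the photograph on day *m*, and the difference is 0.
- OCR dated to the two-week visit, when the investigator decides that no touch-up is needed (day 14): the intervals are those in the table, with the same 14-day difference between the counts.

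**Which count the document supports**

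1. Section 8 has one post-treatment photography visit, Visit 3. The Synopsis, Section 5 and Section 9.1 describe one set of post-treatment photographs, taken one month after OCR. These can only be the Visit 3 photographs.
2. The heading of Section 8.4 names no starting point, so it cannot conflict with sections that do.
3. The heading of Section 8.3 names no starting point either. Its two weeks are understood only by reading the Synopsis and Section 5. The same cross-reading gives the starting point for Visit 3.
4. The four-week sentence has the post-OCR visits as its subject and comes directly after the sentence on touch-ups. Its plural injections can include the touch-up. Counted from Visit 1, it would place a four-week post-OCR visit two weeks after OCR for a touched-up subject, contrary to its own subject and to the three statements above.

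Read together, the passages are consistent.

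**The case for a change.** The strongest case for a change is that the anchor has to be inferred. Neither Section 8.4 nor the four-week sentence names the injection session, and staff scheduling visits may not consult Section 9.1. The photograph cannot be retaken once its time has passed, and a clarifying phrase would cost almost nothing and move no visit at a site that already counts from OCR.

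Much of this is true. The heading is silent, the four-week sentence could be tighter, there is no visit window, and the 14-day arithmetic is right. What does not stand is the step from silence to inconsistency. To get a conflict, one must carry the Visit 2 starting point over to Visit 3 and set aside the text that describes the Visit 3 photographs. Nothing in the document says or suggests that staff would count that way.

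The consequence is also unquantified. The document gives no number of touch-ups among the 20 subjects and no time course for swelling or for the measurements. Neither the size nor the direction of any effect on the paired comparison can be derived. A visit window would be good practice, but its absence contradicts nothing.

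**Conclusion.** The concern does not call for a change. Section 8.4 does not repeat a starting point that the Synopsis, Section 5 and Section 9.1 state. That is a gap in a label, of the kind that anyone reading the whole protocol fills in the same way. Followed as written, the plan has photographs taken one month after OCR, and the planned analysis is unaffected.

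The possible size is a 14-day shortfall (14 days instead of 28, or 16 to 17 instead of 30 to 31) for a subject touched up at week 2, and only if the month were counted from Visit 1. For subjects not touched up, the two counts agree only if OCR is dated to Visit 1, which the document does not state.

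The conclusion rests on reading the one-month visit of Section 8.4 as the post-OCR visit named in the Synopsis, which is the only visit it can be. If the protocol were reopened for another reason, the wording of these sections could be aligned so that each gives the same starting point. That would be editorial.

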6 SUBJECT SELECTION

A total of 20 subjects.

All Subjects must comply with the following inclusion and exclusion criteria:

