8 STUDY PROCEDURES

8.1 Screening Visit

The PI and/or designee is responsible for keeping a record of all subjects screened for entry into the study and those subjects that were excluded, including exclusionary reason.

The following procedures will be performed:

1. The PI and/or designee is responsible to evaluate and confirm that a subject meets inclusionary/exclusionary criteria.
2. Subjects must provide signed informed consent with confirming signature from investigator/site designee.
3. Subject undergo standard 2D digital portrait photography.

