11.3 Analysis Method

The PI's study coordinator will perform all statistical analyses. This is in an effort to avoid any potential bias that could be created by the treating physician participating in the analysis. Given that there is inherent variability even in standardized portrait photography, the decision was made to perform measurements based on facial landmarks and distance ratios. Statistical analysis will be conducted using a paired *t* test.

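### No repeat frames, averaging or measurement-error estimate is planned for the photographic endpoints; three re-posed frames per pose at each visit would be a cheap gain in precision, of a size the documents cannot fix

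*Combined protocol and SAP*

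**What the plan says.** There are two photographic visits. At screening (section 8.1): "Subject undergo standard 2D digital portrait photography". At one month (section 8.4): "Subject will undergo standardized 2D digital portrait photography". Neither gives a number of frames.

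Appendix A lists three poses (frontal, left profile, right profile), each once. It does not mention repeat exposures, re-posing or averaging.

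Section 5 speaks of single images: "From the profile image, baseline nasal projection measurements will be documented". The vermilion ratio likewise comes from one frontal image. The plan does not say which of the two profiles is used, or whether they are averaged.

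The only statement on measurement error is in section 11.3: "Given that there is inherent variability even in standardized portrait photography", followed by the decision to use landmarks and distance ratios. Section 9.2 credits ratios with removing bias from the camera's distance and angle and from lighting.

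The analysis in section 11.3 is a paired t test on 20 subjects. No expected change, SD, measurement error, alpha, sidedness or power is given. For the Z-angle, section 9.1 gives a direction only: "A change in the angle to a more acute value on postoperative photographs would indicate an increase in upper lip projection".

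**The concern.** A pre/post change carries the error of two photographs. If one frame per visit is measured, the error from head position, lip tension and landmark marking enters the change score in full at each visit. With 20 subjects and no control group, the SD of the change largely decides whether a real effect is seen and how wide its confidence interval is.

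The plan's remedy does not reach this error. A ratio cancels image scale. It does not cancel a slightly rotated head, a tenser lip or a misplaced landmark. The Z-angle, one of the two primary measures, is an angle against a Frankfort plane that the photographer levels with a viewfinder grid.

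Section 5 also has each patient evaluated for whether projection increased. Without any estimate of measurement error, an individual change cannot be told from a re-positioning difference.

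**Working it through.** The plan has no power figure to reproduce. The inputs are therefore partly assumed.

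**From the documents:** n = 20 (section 6), one group, paired t test (section 11.3), so 19 degrees of freedom if all pairs are complete.

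**Assumed:** two-sided 5%; mean Z-angle change 1.4 degrees; SD of the true change 1.5 degrees; per-frame error SD e from 0.5 to 2.0 degrees. The 1.4 degrees corresponds to about 1 mm of lip advance at Z = 78 degrees and a lip-to-chin height of 40 mm: 40/tan 78° = 8.50 mm; 78° − arctan(40/9.50) = 1.36°. At 30 mm and 50 mm it is 1.81° and 1.09°.

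**Formula.** With k frames per visit and a share v of the error variance common to all frames of a visit,

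SD of change = √(1.5² + 2e²[v + (1 − v)/k]).

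Power comes from the noncentral t. The 95% CI half-width is 2.093 × SD/√20.

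**Worked case, e = 1.5, v = 0.** One frame: √(2.25 + 4.50) = 2.60; half-width 1.22; power 63%. Three frames: √(2.25 + 1.50) = 1.94; half-width 0.91; power 87%.

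| e (degrees) | v | SD, 1 → 3 frames | Power, 1 → 3 frames |
|---|---|---|---|
| 0.5 | 0 | 1.66 → 1.56 | 95% → 97% |
| 0.7 | 0 | 1.80 → 1.60 | 91% → 96% |
| 1.5 | 0 | 2.60 → 1.94 | 63% → 87% |
| 2.0 | 0 | 3.20 → 2.22 | 46% → 76% |
| 1.5 | 0.5 | 2.60 → 2.29 | 63% → 74% |
| 1.5 | 0.8 | 2.60 → 2.48 | 63% → 67% |

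**Scale-free version, for Goode's ratio and the vermilion ratio.** Divide both SDs by the expected change. With v = 0 and a true-change SD of 0.5 to 2 times the expected change, three frames add about 9 to 22 points of power if the error SD equals the expected change, about 0 to 5 points if it is half, and about 1 point at most if it is a quarter.

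**Individual changes.** A natural cut-off built from repeat frames is 1.96 × √2 × SD/√3, with SD the within-visit SD. That SD estimates only e√(1 − v). The error in an unchanged subject's difference of means has SD √2 × e√(v + (1 − v)/3). So the cut-off sits at

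1.96 × √{[(1 − v)/3] / [v + (1 − v)/3]}

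standard errors: 1.96 at v = 0, 0.98 at v = 0.5, 0.54 at v = 0.8. The chance that an unchanged subject exceeds it in either direction is 5%, 33% and 59%. Half of each lies in the direction of an increase.

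**The case against.** **The frame count is an inference.** A reader might infer that the protocol fixes one frame per pose. It does not: sections 8.1 and 8.4 order a photography session, Appendix A lists poses rather than exposures, and the Appendix B diagram is not readable here. The singular wording supports one measured image per endpoint and no more. This stands. It does not remove the point, because no repeat or averaging is specified anywhere.

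**The size of the error is unknown.** A reader might also infer that pose and marking error is about as large as the expected change. The documents give neither quantity, so this is an assumption. If the error is small, the gain is a few points at most. This stands.

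**Averaging does not remove shared error.** Frames from one session share the set-up, habitual posture and the person marking, so some sharing is plausible. This stands, and the last two rows of the table show its effect.

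**Controls already exist.** Appendix A requires a levelled Frankfort plane, a marked camera position, a relaxed face with closed lips and a rotation check. These lower the error but do not estimate it.

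**Two profiles are already taken.** Their use is not stated, they do not show how much a re-posed subject varies, and the frontal view has no second side.

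**Conclusion.** The point holds as a low-cost improvement in precision. It does not show that the paired t test is invalid: random error costs power and width, not validity. The plan admits photographic variability, offers a remedy that leaves pose, lip-tension and marking error in place, and provides no means of estimating that error.

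The benefit cannot be fixed from the documents. Under the Z-angle assumptions above it runs from 2 points of power (e = 0.5) to 30 points (e = 2.0) with independent errors. At e = 1.5 it falls from 24 points to 11 or 4 when half or 80% of the error variance is shared within a visit. In none of these cases does averaging lower power.

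A reader might take the repeat frames as licence to classify individual subjects as increased. They do not support that: frames from one sitting do not capture error between visits a month apart, and the within-visit SD is only a lower bound on measurement error.

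**What to change.** - **Appendix A, 8.1 and 8.4:** take three frames of each pose at both photographic visits, with the subject stepping off the mark and re-posing between frames. State which profile, or both, enters the analysis.
- **11.3:** mark each frame independently, without sight of the marks on the other frames. Use the mean per subject per visit in the paired t test. Report the within-visit SD of each measure, labelled as a lower bound on measurement error.
- **Individual changes:** do not use 1.96 × √2 × SD/√3 as a threshold for an individual increase.
- **Power:** any statement of the gain should be given as conditional on assumed error sizes, with a range.

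Cost: a few minutes per visit, and 20 subjects × 2 visits × 3 poses × 3 frames = 360 images to mark instead of 120. No extra visits or subjects. The change must be in place before baseline photography, since pre-treatment frames cannot be retaken after injection.
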